9.2 SETTING

This retrospective database study will leverage the GE EMR data from October 1, 2013 to April 30, 2018. The EMR consists of patient data from ambulatory care records in the US and is representative of the US population receiving healthcare in the ambulatory setting. Patients will be included in one of three study cohorts based on prescription history from October 1, 2014 to April 30, 2018, allowing for a 12-month pre-index period to describe patient demographic, clinical and treatment characteristics.

Index date

The index date for the nintedanib (or pirfenidone) cohort will be the date of the first nintedanib (or pirfenidone) prescription during the selection window (from October 1, 2014 to April 30, 2018). The index date for the untreated cohort will be the date of the earliest IPF diagnosis or a randomly assigned date between October 1, 2013 and April 30, 2018.

Pre-index period

[figure not shown]
The pre-index period for each cohort will be the 12 months prior to the index date. Patients will be required to have ≥ 1 diagnosis of IPF during the pre-index period (see additional inclusion criteria described below).

Post-index period

The post-index period for each cohort will start from the index date. Since the study aims to evaluate patient characteristics during the pre-index period, no minimum follow-up will be required for post-index period and no study measures will be assess during the post-index period.

Patient selection is illustrated in Figure 1.

Figure 1. Patient Selection

Nintedanib cohort

Inclusion criteria:

- With ≥ 1 diagnosis for IPF (the International Classification of Diseases, Ninth Revision, Clinical Modification [ICD-9-CM] codes 516.3, 516.31, 515,¹¹ or ICD-10-CM codes J84.112) in the EMR between October 1, 2013 to April 30, 2018
- With ≥ 1 prescription for nintedanib between October 1, 2014 and April 30, 2018 (the selection window)
 - The date of the first prescription will be defined as the index date
- With ≥ 1 record in the EMR database during the 12 months prior to the index date (the pre-index period)
- With ≥ 1 diagnosis of IPF during the 12 months prior to the index date
- Age ≥ 40 on the index date
- will explore also requiring ≥ 1 chest CT scan before first IPF diagnosis during the pre-index period¹²

Exclusion criteria:

- With ≥ 1 diagnosis of other known causes of interstitial lung disease (ILD) on the date of or after the first IPF diagnosis during the pre-index period^{12,13}

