- Other known causes of ILD include conditions such as systemic sclerosis, rheumatoid arthritis, systemic lupus erythematosus, dermatomyositis, polymyositis, Sjögren disease, and hypersensitivity pneumonitis (ICD-9-CM codes 135, 237.7, 272.7, 277.3, 277.8, 446.21, 446.4, 495, 500–505, 506.4, 508.1, 508.8, 516.0, 516.1, 516.32–516.37, 516.2, 516.8, 516.9, 517.0, 517.2, 517.8, 518.3, 555, 710.0, 710.0–710.4, 714.0, 714.81, 720, and 759.5, or ICD-10-CM equivalent codes)^{12,13}
- With ≥ 1 prescription for nintedanib prior to the index date
- With ≥ 1 prescription for pirfenidone prior to or on the index date

Pirfenidone cohort

Inclusion criteria:

- With ≥ 1 diagnosis for IPF (ICD-9-CM codes 516.3, 516.31, 515,¹¹ or ICD-10-CM codes J84.112) in the EMR between October 1, 2013 to April 30, 2018
- With ≥ 1 prescription for pirfenidone between October 1, 2014 and April 30, 2018 (the selection window)
 - The date of the first prescription will be defined as the index date
- With ≥ 1 record in the EMR database during the 12 months prior to the index date
- With ≥ 1 diagnosis of IPF during the 12 months prior to the index date
- Age ≥ 40 on the index date
- will explore also requiring ≥ 1 chest CT scan before first IPF diagnosis during the pre-index period¹²

Exclusion criteria:

- With ≥ 1 diagnosis of other known causes of interstitial lung disease (ILD) on the date of or after the first IPF diagnosis during the pre-index period^{12,13}
 - Other known causes of ILD include conditions such as systemic sclerosis, rheumatoid arthritis, systemic lupus erythematosus, dermatomyositis, polymyositis, Sjögren disease, and hypersensitivity pneumonitis (ICD-9-CM codes 135, 237.7, 272.7, 277.3, 277.8, 446.21, 446.4, 495, 500–505, 506.4, 508.1, 508.8, 516.0, 516.1, 516.32–516.37, 516.2, 516.8, 516.9, 517.0, 517.2, 517.8, 518.3, 555, 710.0, 710.0–710.4, 714.0, 714.81, 720, and 759.5, or ICD-10-CM equivalent codes)^{12,13}
- ≥ 1 prescription for pirfenidone prior to the index date
- ≥ 1 prescription for nintedanib prior to or on the index date

Untreated cohort

Inclusion criteria:

- With ≥ 1 diagnosis for IPF (ICD-9-CM codes 516.3, 516.31, 515,¹¹ or ICD-10-CM codes J84.112) in the EMR between October 1, 2013 to April 30, 2018
 - Index date will be defined as the date of the earliest IPF diagnosis or a randomly assigned date based on the exploratory analyses to be performed on the two treatment cohorts (exploring time from IPF diagnosis to treatment initiation)

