9.3 VARIABLES

9.3.1 Exposures

Both nintedanib (Ofev, BI) and pirfenidone (Esbriet, Genentech) were approved by the US FDA on October 15, 2014 (reflected by start of selection window in this study). Nintedanib initiators will be identified using prescription records for nintedanib, with the index date being the first prescription in the EMR during the selection window. Similarly, pirfenidone initiators will be identified using prescription records for pirfenidone; index date is first prescription. New users of these medications will be selected into the study, excluding those who initiated both medications on index. The number of patients who initiated both medications on index will be reported during the patient attrition. Since the purpose of this study is to identify predictors of IPF treatment initiation, no post-index follow-up measures will be reported. Patients who switched between the treatments during the pre-index period will be excluded because of the new user design, and those who switch after the index date will not be a concern as no study measures will be evaluated during the post-index period for the objectives of this study. No validation will be performed on the exposures of interest as exposure ascertainment relies on evidence of ≥ 1 prescription record.

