9.5 STUDY SIZE

A preliminary feasibility assessment of the most recent EMR data indicates the presence of 2,499 patients newly starting on an IPF treatment (Table 1). 64% of patients are 40 years or above, of which 76% had at least one pulmonary function test. An early feasibility assessment estimated that about 10,000 IPF patients were not treated with antifibrotics.

Considering the orphan nature of IPF and recent FDA approval of these two drugs (within last three years), the EMR database is a good source to extract such a population as it continues to grow. The IPF patients counts are reflective of national estimates (6.8–8.8 per 100,000; <0.01%). The availability of patients should provide sufficient sample to estimate standardized differences in patient characteristics between three cohorts.

Table 1. Preliminary Patient Counts (will vary once study selection criteria are applied, as outlined in Section 9.2)

	Characteristics	Number of patients
1	Evidence of IPF treatment (pirfenidone or nintedanib) between October 1, 2014 to March 30, 2018), first date is index	2,750
2	In #1 with ≥ 1 EMR before index date	2,508
3	In #2 with no evidence of pirfenidone or nintedanib before index date	2,499
4	In #3 with diagnosis of IPF (ICD-9-CM codes 516.3x, 515, or ICD-10-CM codes J84.112) before index date	2,061
5a	In #4 and with prescription for (mutually exclusive): Pirfenidone only Nintedanib only Both Pirfenidone and Nintedanib	1,627 868 615 144
5b	In #4 and age ≥ 40 years	1,623
5c	In #4 with at least one PFT observations (FEV1, FVC, TLC, Oxygen saturation, OR DCCO) (with non-missing test results) BEFORE index	1,231
6a	In 5c with at least one oxygen saturation value	1,150
6b	In 5c with at least one DCCO value	293

Characteristics		Number of patients
6c	In 5c with at least one TLC value	217
6d	In 5c with at least one FEV/FVC value	627

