9.12 BIAS

To minimize the bias resulting from treatment switching, study selection for new initiators will be used to exclude patients with nintedanib or pirfenidone use prior to index. In addition, an algorithm for IPF identification adapted from claim-based algorithms (see Section 9.2) will be used for the untreated cohort to minimize the bias resulting from misclassifying patients as having IPF or not.^{12,13}

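### New use rests on as little as one visit before index, so a patient who started an antifibrotic outside the network can be counted as an initiator

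*Combined protocol and SAP*

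**What the plan says.** Section 9.2 defines the index date for each treated cohort as "the date of the first nintedanib (or pirfenidone) prescription during the selection window (from October 1, 2014 to April 30, 2018"). The same section states that the study "will leverage the GE EMR data from October 1, 2013 to April 30, 2018". Section 9.3.1 notes that both drugs "were approved by the US FDA on October 15, 2014 (reflected by start of selection window in this study").

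Each treated cohort has two drug-history exclusions in 9.2:

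- **Same drug:** "With ≥ 1 prescription for nintedanib prior to the index date" for the nintedanib cohort and "≥ 1 prescription for pirfenidone prior to the index date" for the pirfenidone cohort.
- **Other drug:** any prescription for it before or on the index date.

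The history criteria for treated patients are at least one EMR record and at least one IPF diagnosis in the 12 months before index. The plan sets no minimum time in the database and no drug-free observed interval. Section 9.3.1 adds that exposure will not be validated.

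Section 9.12 relies on this selection: "study selection for new initiators will be used to exclude patients with nintedanib or pirfenidone use prior to index". Section 9.9 acknowledges that a recorded prescription may not have been filled or taken. It does not mention treatment begun where the database cannot see it.

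**The concern.** The Abstract calls the 12-month baseline pre-treatment, and the study's purpose is to find characteristics that drive the choice of drug. Both depend on treated patients really being new users. For a patient already on treatment, several planned baseline variables in 9.3.3 would be measured on drug:

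- **Lung function.** FVC and the FVC-based GAP index are compared between cohorts, while Section 7 reports that both drugs reduce FVC decline.
- **Liver tests.** Any baseline history of high ALT, AST or total bilirubin overrides the value nearest to index, so one on-drug abnormality sets the category.
- **Time from earliest IPF diagnosis to index.** This is wrong if the true start was elsewhere. Section 9.2 may use the same distribution to assign untreated index dates, so the error can reach the comparator cohort.

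A consequence of the drug could then be read as a reason for prescribing it. The setting makes this plausible. Section 9.4 describes a network of primary care practices with about 456 pulmonologists among more than 43,000 providers (456 / 43,000 = about 1%), so treatment started by an outside specialist and later recorded in the network is a realistic path.

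**Working it through.** **1. What the same-drug exclusion can catch.** Inputs are the index rule and window (9.2), the approval date (9.3.1) and the data start (9.2).

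- Index is the earliest prescription of the drug on or after October 1, 2014.
- A prescription of the same drug before index must therefore be dated before October 1, 2014. The data start on October 1, 2013, so it falls in the 365 days before the window opens.
- Approval was on October 15, 2014, which is 14 days after the window opens. Every record this line could catch predates approval.
- For post-approval prescriptions held in the database, the first-prescription rule already does the work. The other-drug exclusion is different: it does remove patients within the window.

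**2. What the history criteria require.** Suppose a patient already treated elsewhere has a first network visit coded IPF, with no drug recorded, and a first network prescription a week later. That first visit supplies both the record and the diagnosis. The index rule sees no earlier prescription, and neither exclusion fires. A patient who began the other drug outside the network and then switched passes in the same way.

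**3. Table 1 (Section 9.5).** The counts are database output and cannot be re-derived, but the step losses can:

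| Step | Calculation | Removed |
|---|---|---|
| Some EMR record before index | 2,750 − 2,508 | 242 (8.8%) |
| "In #2 with no evidence of pirfenidone or nintedanib before index date" | 2,508 − 2,499 | 9 (0.36%) |
| IPF diagnosis before index | 2,499 − 2,061 | 438 (17.5%) |

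The no-prior-drug step removes very few, as step 1 would suggest. It pools both drugs, however, so it is not a direct test of the same-drug line.

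**4. How large the effect could be.** The share of continuing users is not given. An assumed 2% to 20% would be 12 to 123 of 615 nintedanib patients and 17 to 174 of 868 pirfenidone patients.

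Let m be that share and D the difference between continuing users and true initiators on a variable, in SD units. The cohort mean moves by m × D, so the standardized difference moves by about m × D, ignoring the small change in the cohort SD.

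- Treated versus untreated: 0.10 × 1.0 = 0.10, or 0.20 × 0.5 = 0.10, which is the plan's threshold. With m = 0.05 and D = 0.5 the shift is 0.025.
- Nintedanib versus pirfenidone, if both drugs move the variable alike: the shift is D × (m1 − m2). Reaching 0.10 needs a gap in shares of 0.10 / D, which is 40, 20 or 10 percentage points for D = 0.25, 0.5 or 1.0.

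**5. Precision for comparison.** From the 9.7.1 formula at d = 0, the standard error is √[(615 + 868) / (615 × 868)] = 0.0527. The 95% half-width is 1.96 × 0.0527 = 0.103.

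**The case against.** A redundant exclusion is not itself a defect. It admits nobody: with or without it, a prescription written outside the network is invisible, and the index rule already secures new use for everything the database holds. That is correct, and the point rests only on the thin history requirement.

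The leak is also narrow. It needs an earlier visit coded IPF, no drug recorded at that visit, and a later network prescription. The record rule removed 242 patients in the feasibility count and the diagnosis rule another 438. A reader might take the 242 as evidence of prevalent use, but they were excluded, and a newly referred patient whose first recorded event is a genuine first prescription looks the same.

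The two drugs share an approval date and parallel rules, and nothing in the documents suggests unequal shares of continuing users. The comparison between drugs is therefore less exposed than those with untreated patients. A smaller shift could still tip a variable near the threshold.

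Finally, a strict 12-month history as the main definition would do harm. Data begin on October 1, 2013, so a patient indexed on October 15, 2014 would need a first record between October 1 and 15, 2013. The rule would strip out early post-approval initiators, who are least likely to be continuing users, and distort the planned description over time. This stands, and it shapes the fix.

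None of it answers the missing observation requirement or the silence of 9.9.

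**Conclusion.** The gap is real and follows from the text: one visit shortly before index can satisfy every history criterion, so a patient treated outside the network can be labelled a new initiator. The number affected cannot be found from the documents, and the shifts shown rest on assumed shares and assumed on-drug differences. They show that the treated versus untreated ASDs could reach the 0.10 threshold under substantial contamination, not that they will.

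Two stronger readings are tempting and not supported. One is that continuing users are known to be in the cohorts in some given proportion; the documents show only that they can be. The other is that 9.12 credits the same-drug line with removing prior use; it credits the new-initiator selection as a whole. What 9.12 lacks is a statement that this selection works only on treatment the database records.

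**What to change.** Keep the current definition as primary and make three additions.

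1. **Section 9.7.1:** a sensitivity analysis repeating the three ASD comparisons and both propensity models, with treated patients restricted to those who meet both conditions:
   - the first EMR record is at least 12 months before index, or is before October 15, 2014 (the second route keeps early initiators observed since before approval);
   - there is no earlier prescription or medication-list entry for either drug.
2. **Reporting:** time from first EMR record to index by cohort, and the number the restriction removes as a row in the attrition table.
3. **Sections 9.9 and 9.12:** a sentence stating that antifibrotic treatment started outside the network is not visible, so some apparent initiators may be continuing users or switchers.

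The cost is a date filter and a medication check on data already held, plus a second run of the planned tables and models. Treated cohorts will be smaller in that analysis. If a share r of each drug cohort is retained, the nintedanib versus pirfenidone half-width grows from 0.103 to about 0.103 / √r. The restriction is also imperfect: a patient with an old network record who was later treated elsewhere would still pass, so the disclosure is needed whatever the analysis shows.

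### The IPF case definition changes scope between ICD-9 and ICD-10 and the untreated index window is inconsistent, so the mix of code systems may differ between treated and untreated patients

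*Combined protocol and SAP*

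**What the plan says.** All three cohorts in Section 9.2 use one inclusion list: "ICD-9-CM codes 516.3, 516.31, 515" "or ICD-10-CM codes J84.112". All three also share one diagnosis window, "in the EMR between October 1, 2013 to April 30, 2018". The exclusion list for other interstitial lung disease, which contains 516.32 to 516.37, is carried forward with the words "or ICD-10-CM equivalent codes"; the inclusion list has no such clause. The feasibility count in Section 9.5, Table 1, uses a slightly different list: "with diagnosis of IPF (ICD-9-CM codes 516.3x, 515, or ICD-10-CM codes J84.112) before index date".

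Index windows differ. Treated patients are indexed at their first prescription "during the selection window (from October 1, 2014 to April 30, 2018". For untreated patients the index-date paragraph allows the earliest IPF diagnosis or "a randomly assigned date between October 1, 2013 and April 30, 2018". The untreated inclusion criteria leave the choice open: "Index date will be defined as the date of the earliest IPF diagnosis or a randomly assigned date based on the exploratory analyses".

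Other parts point to 2014 for everyone. The opening paragraph of Section 9.2 builds all three cohorts on prescription history from October 1, 2014, and the index-year categories in Section 9.3.3, which apply to all cohorts, begin at 2014.

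Treated patients must have an IPF diagnosis in the 12 months before index. Sections 9.3.3 and 9.7.1 plan no tabulation or analysis by qualifying code.

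**The concern.** The plan's own lists show the change of scope. Because 516.32 to 516.37 count as other disease, 516.31 is the specific code, 516.3 is its parent, and 515 lies outside that family. No ICD-10 counterpart is named for 515 or for unspecified 516.3. Patients who enter on those codes under ICD-9 have no stated route in under ICD-10.

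If the share of ICD-9 diagnoses differs between cohorts, part of a baseline difference may reflect how IPF was coded rather than who was treated. Untreated patients are the more exposed group: a treated patient also has an antifibrotic prescription, while an untreated patient is identified by codes alone. Two of the three primary comparisons (Section 9.3.2.1) and one of the two propensity models (Section 9.3.2.2) involve the untreated cohort. An absolute standardized difference (ASD) of 10% is to be read as meaningful, and the results are meant to identify what drives treatment selection.

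**Working it through.** The plan gives no figure to reproduce. The relevant quantity is the share of qualifying diagnoses recorded under ICD-9.

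**Inputs from Section 9.2.** Untreated index window October 2013 to April 2018: 55 months (1,673 days). Treated index window October 2014 to April 2018: 43 months (1,308 days). Treated look-back for the diagnosis: 12 months.

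**Assumptions, not in the documents.** One changeover date, uniform index dates, and diagnoses spread evenly over the look-back.

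**Formulas.** Let m be the months from October 2014 to the changeover and L the look-back in months.
- Treated: (m + L/2)/43
- Untreated, index = diagnosis: (m + 12)/55
- Untreated, random index with the same look-back: (m + 12 + L/2)/55

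With L = 12:

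| Changeover | Untreated, index = diagnosis | Untreated, random index | Treated | Excess, index = diagnosis | Excess, random index |
|---|---|---|---|---|---|
| Oct 2014 (m = 0) | 12/55 = 21.8% | 18/55 = 32.7% | 6/43 = 14.0% | +7.9 | +18.8 |
| Oct 2015 (m = 12) | 24/55 = 43.6% | 30/55 = 54.5% | 18/43 = 41.9% | +1.8 | +12.7 |
| Oct 2016 (m = 24) | 36/55 = 65.5% | 42/55 = 76.4% | 30/43 = 69.8% | −4.3 | +6.6 |

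Excesses are in percentage points, taken before rounding. Counting days instead of months changes them by no more than 0.1 point.

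**Shorter look-back, October 2015, untreated index = diagnosis.** With L = 1, 3 or 6 the treated share is 29.1%, 31.4% or 34.9%, an excess of 14.6, 12.2 or 8.8 points. If the diagnosis falls at the prescription (L = 0), it is 12/43 = 27.9%, an excess of 15.7. Hence about 2 to 16 points.

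**Rising uptake.** If treated index dates increase linearly over the window, the treated share with a 12-month look-back falls to 18.2%, and the excess becomes 43.6 − 18.2 = 25.4 points.

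**Common start in October 2014, changeover October 2015.** Untreated becomes 12/43 = 27.9% (index = diagnosis) or 18/43 = 41.9% (random index), against 41.9% treated. The excess is −14.0 or 0.

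**Reaching the 10% threshold.** If ICD-9-qualified and J84.112-qualified patients differ by D standard deviations on some characteristic, equally in both cohorts, an excess Δ alone produces an ASD of about Δ × D. An ASD of 0.10 needs D = 0.10/0.157 = 0.64 at the top of the 2-to-16 range, 0.10/0.127 = 0.79 under the random index, and 0.10/0.018 = 5.6 at the bottom.

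**The case against.** The strongest objection is that code list and diagnosis window are the same for every cohort, and that the treated look-back also reaches to October 2013. That stands, and it rules out a tempting stronger reading. A reader might compare the windows by index date, obtain 21.8% against 0%, 43.6% against 27.9% and 65.5% against 55.8%, and conclude that the untreated cohort relies on the wider definition by 10 to 22 points. That calculation uses the treated prescription date, whereas the code system is fixed by the earlier qualifying diagnosis. With the full look-back and untreated index = diagnosis, the excess runs from about +8 to −4 points.

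It is also fair to say that the 2013 start is itself contradicted in Sections 9.2 and 9.3.3, and that an untreated index in the first year cannot have a full 12-month baseline in data that begin on October 1, 2013. This makes the 55-month window doubtful, but it is a reason to reconcile the text, since the code mix depends on the answer.

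Some protection exists. Other interstitial lung disease is excluded in all cohorts, index year is a listed measure, and Section 9.12 says a case-finding algorithm will be applied to untreated patients. Section 9.2, however, only undertakes to explore the two-diagnosis and CT requirements, and none of these measures shows who entered through 515 or 516.3.

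A reader might also want code system as a covariate in the propensity model. It would largely duplicate index year, it is not a patient characteristic, and it would not correct a misclassified diagnosis.

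**Conclusion.** The concern holds in limited form. The inclusion list changes scope with the code system, the untreated index window is stated inconsistently, and no planned analysis would show whether either matters. The code mix may therefore differ between treated and untreated patients.

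Neither size nor direction is established. With an October 2015 changeover and uniform index dates, the untreated excess is about 2 to 16 points (index = diagnosis) or about 13 points (random index, same look-back). Within the changeover dates tested, the order reverses only for a late date combined with index = diagnosis and a long treated look-back. Rising uptake would widen the gap. The number qualifying only through 515 or 516.3 is not documented, so the effect on any ASD is unknown; the window mechanism alone would need a fairly large difference between the two kinds of patient to reach 10%.

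The point concerns nintedanib versus untreated, pirfenidone versus untreated, and the treated-versus-untreated propensity model. Nintedanib and pirfenidone share the same index window, so the window difference does not affect their comparison.

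**What to change.** 1. Start the untreated index window on October 1, 2014, as for the treated cohorts, and reconcile the index-date paragraph of Section 9.2 with its opening paragraph and with the index-year categories in Section 9.3.3. Settle the untreated index rule at the same time. A common start equalises the code mix under a random index with the same look-back, but under index = diagnosis it could leave untreated patients up to 14 points lower.
2. Tabulate, per cohort, the patients who qualify only through 515 or 516.3.
3. Pre-specify a sensitivity analysis that repeats the ASDs and the treated-versus-untreated propensity model in patients with 516.31 or J84.112 only. State whether untreated index dates are re-derived from those codes. Align the ICD-9 list in Table 1 with Section 9.2.

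Cost: one table and one further run on data already held. The common start gives up untreated index dates before October 2014, which are 12/55 = 21.8% of that window if uniform and lack a full baseline anyway. The restricted run shrinks all three cohorts, including the treated ones (868 and 615 before final selection). By the standard-error formula in Section 9.7.1, an ASD of 0.10 for 615 against 10,000 has a 95% half-width of 1.96 × √(10,615/6,150,000 + 0.01/21,230) = 0.08. If half of each cohort remained (an assumption), it would be 0.08 × √2, about 0.12. The run should therefore be judged by how far the ASDs move, not by re-applying the 10% cut-off.

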 - will explore requiring ≥ 2 diagnoses for IPF that are ≥ 30 days apart to improve the identification of IPF patients^{12,13}
- With ≥ 1 record in the EMR database during the 12 months prior to the index date (the pre-index period)

- Age ≥ 40 on the index date
- will explore also requiring ≥ 1 chest CT scan before first IPF diagnosis during the pre-index period¹²

Exclusion criteria:

- With ≥ 1 diagnosis of other known causes of interstitial lung disease (ILD) on the date of or after the first IPF diagnosis during the pre-index period
 - Other known causes of ILD include conditions such as systemic sclerosis, rheumatoid arthritis, systemic lupus erythematosus, dermatomyositis, polymyositis, Sjögren disease, and hypersensitivity pneumonitis (ICD-9-CM codes 135, 237.7, 272.7, 277.3, 277.8, 446.21, 446.4, 495, 500–505, 506.4, 508.1, 508.8, 516.0, 516.1, 516.32–516.37, 516.2, 516.8, 516.9, 517.0, 517.2, 517.8, 518.3, 555, 710.0, 710.0–710.4, 714.0, 714.81, 720, and 759.5, or ICD-10-CM equivalent codes)^{12,13}
- With prescription for nintedanib or pirfenidone anytime during the data window

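### The untreated index date is left open between two rules: the earliest-diagnosis option conflicts with the plan's own pre-index criteria, and both options allow dates before the selection window

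*Combined protocol and SAP*

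**What the plan says.** All references are to the combined protocol and SAP.

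- **Untreated index date (9.2).** The index-date paragraph gives "the date of the earliest IPF diagnosis or a randomly assigned date between October 1, 2013 and April 30, 2018". The untreated inclusion list says "Index date will be defined as the date of the earliest IPF diagnosis or a randomly assigned date based on the exploratory analyses", and explains that these analyses look at time from diagnosis to treatment start in the two drug cohorts. No threshold, distribution or assignment procedure follows.
- **Treated index date (9.2).** First prescription between October 1, 2014 and April 30, 2018.
- **Diagnosis before index (9.2).** The pre-index paragraph, which covers every cohort, states "Patients will be required to have ≥ 1 diagnosis of IPF during the pre-index period". Both treated lists repeat it: "With ≥ 1 diagnosis of IPF during the 12 months prior to the index date". The untreated list does not.
- **Other-ILD exclusion (9.2).** All three lists exclude other known causes of ILD coded "on the date of or after the first IPF diagnosis during the pre-index period".
- **Post-index period (9.2).** "The post-index period for each cohort will start from the index date", and "no study measures will be assess during the post-index period".
- **Covariate windows (9.3.3).** Most measures cover 12 months including the index date, but treatment history excludes it. Time from earliest diagnosis to index is listed only for the two drug cohorts. Index-year categories run from 2014 to 2018.
- **Context.** Section 9.3.1 dates approval of both drugs to October 15, 2014 and gives the purpose as finding predictors of treatment initiation. Section 9.7.1 treats an ASD of at least 10% as meaningful.

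**The concern.** The index date fixes every baseline window in the untreated cohort. With two rules open and no decision rule, the choice can be made after data have been seen, and the two rules give different baselines.

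Under the earliest-diagnosis rule, window placement is tied to cohort. A treated patient's 12 months must include a recorded IPF diagnosis, whereas an untreated patient's 12 months end at the first one. Covariates that depend on care for known disease (steroids, oxygen, rehabilitation, HRCT, biopsy) can then differ because of where the window sits and not because they drive initiation. Two of the three primary contrasts (each drug versus untreated) and the treated-versus-untreated propensity comparison are exposed. Because time since diagnosis is not reported for untreated patients, a reader could not see the imbalance.

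Separately, an untreated patient indexed before October 2014 has a truncated look-back and is compared at a time when neither drug was approved.

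**Working it through.** The plan states no figure on this point to reproduce. The check sets its rules side by side, then uses its own dates and formulas.

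**1. Earliest diagnosis against the pre-index diagnosis rule.** If index is the earliest recorded diagnosis, no recorded diagnosis precedes it. If the index day is outside the pre-index period, as the post-index paragraph implies, no untreated patient can meet the rule. If the index day is inside, as Section 9.3.3 has it for most covariates, every untreated patient meets it automatically. Either way it does not do for untreated patients what it does for treated ones.

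**2. Earliest diagnosis against the other-ILD exclusion.** The search starts at the first IPF diagnosis in the pre-index period. Where that is the index day, the search covers 0 or 1 day, against up to 12 months for a treated patient. Letting it run past index would fit poorly with the statement that nothing is assessed post-index.

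**3. Dates.** October 1, 2013 to April 30, 2018 inclusive is 4 × 365 + 1 (leap day) + 212 = 1,673 days.

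| Part of the range | Days | Share of days |
|---|---|---|
| Before October 1, 2014 (selection window; full 12-month look-back) | 365 | 21.8% |
| Before October 15, 2014 (approval) | 379 | 22.7% |
| In 2013 (no index-year category) | 92 | 5.5% |

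**4. How small a shift reaches the threshold.** Section 9.7.1 gives d = (p1 − p2) / √{[p1(1 − p1) + p2(1 − p2)]/2}. Setting d = 0.10 and solving for p1, with p2 assumed:

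| p2 | p1 | Shift (percentage points) |
|---|---|---|
| 5% | 7.41% | 2.4 |
| 10% | 13.20% | 3.2 |
| 20% | 24.14% | 4.1 |
| 30% | 34.67% | 4.7 |
| 50% | 54.99% | 5.0 |

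**5. Illustrations, on assumptions.** Suppose the window up to diagnosis captures 75% of what a later window would. A covariate at 20% in treated patients is then recorded in 15% of untreated patients: d = 0.05 / √[(0.16 + 0.1275)/2] = 0.13. At 10% prevalence d = 0.089, below the threshold.

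For truncation alone, assume index dates uniform over the range, a constant event rate and no true difference. With 12-month prevalence p and λ = −ln(1 − p), mean capture in a look-back uniform on 0 to 12 months is 1 − p/λ. Mixing 21.8% of that with 78.2% at p gives d = 0.037, 0.068, 0.097 and 0.154 for p = 10%, 30%, 50% and 80%.

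**6. Precision if untreated patients are lost.** The half-width is 1.96 × √[(n1 + n2)/(n1 n2) + d²/(2(n1 + n2))]. The preliminary counts in the Abstract are 615 nintedanib, 868 pirfenidone and about 10,000 untreated. At d = 0.10:

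| Drug cohort | n2 = 10,000 | n2 = 5,000 |
|---|---|---|
| Nintedanib, n1 = 615 | 0.081 | 0.084 |
| Pirfenidone, n1 = 868 | 0.069 | 0.072 |

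**The case against.** The strongest reply is that the choice is not arbitrary. The untreated list names the analysis meant to inform it, and a random date built from diagnosis-to-initiation times would avoid the pre-diagnosis problem. The pre-index diagnosis rule, read with the index day excluded, would itself rule out the earliest-diagnosis option. The 2013 start looks like a drafting slip, since Section 9.2 bases cohort entry on prescription history from October 1, 2014 so as to allow a 12-month look-back, and the index years begin in 2014. This stands to the extent that a basis is named. But a basis is not a rule, and the text still permits the option that its own criterion excludes. Figure 1 is not available here and might add detail, but it would not remove the conflict in the text.

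The contrast between windows is also less than complete. A treated patient diagnosed shortly before the prescription has a mostly pre-diagnosis baseline too, most untreated covariates include the diagnosis day, and the earliest diagnosis means the earliest in data from October 2013. These points stand. Treatment history, which excludes the index day, remains the most exposed.

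Section 9.2 would also explore a chest CT requirement and, for untreated patients, "will explore requiring ≥ 2 diagnoses for IPF that are ≥ 30 days apart to improve the identification of IPF patients". These could partly offset the weaker ILD exclusion, but neither is committed to. The threshold shifts in the working are a property of the ASD formula; they do not show that this rule produces such a shift.

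**Conclusion.** The point holds and should be corrected before any untreated comparison. As written, the untreated index date can follow a rule that contradicts the pre-index diagnosis requirement, nearly empties the ILD exclusion and misaligns the baseline windows. It can also fall before the selection window and before approval. Both drug-versus-untreated primary contrasts and the treated-versus-untreated propensity model are affected. Nintedanib versus pirfenidone is not.

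Three stronger readings are tempting and are not supported:

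- **About 22% of untreated patients would be indexed too early.** The 21.8% and 22.7% are shares of calendar days. Patient shares are unknown, and the requirement of at least one EMR record in the 12 months before index removes some of the earliest dates.
- **Untreated baselines lie wholly before diagnosis and treated baselines wholly after.** Both can be mixed, as set out above.
- **The bias has a known size or direction.** It cannot be computed from the documents. HRCT and biopsy, for instance, may be well captured in the year leading to diagnosis, while sex, race and region should hardly move.

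The window-misalignment conclusion depends on the earliest-diagnosis option being used. The date conclusion applies to that option and to the random date as the index-date paragraph states it; the untreated list gives no range for its random date.

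**What to change.** In Section 9.2:

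1. Delete the earliest-diagnosis option.
2. Limit untreated index dates to October 1, 2014 to April 30, 2018, as for treated patients. This leaves 14 pre-approval days, but the same 14 in every cohort.
3. Before any untreated comparison, commit to one diagnosis-anchored rule that aligns time since diagnosis and calendar time with treated patients. Examples are first diagnosis plus an interval drawn from treated patients diagnosed in a similar period, or matching on time since diagnosis. A single pooled draw would fit poorly: a patient diagnosed on October 1, 2013 and treated after approval has an interval of at least 379 days, which cannot fit an untreated patient first diagnosed after April 16, 2017.
4. Apply the 12-month IPF-diagnosis criterion and the other-ILD exclusion identically to all three cohorts. State whether the index day counts and when the ILD search ends.

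In Section 9.3.3, report time from earliest diagnosis to index for all three cohorts.

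The cost is wording, programming and some untreated patients. Those lost would include long draws (past April 30, 2018 or, beyond 12 months, with no repeat IPF code) and, among patients diagnosed before October 2014, draws too short to reach the window. Donors are sparse at the end: the stretch from October 1, 2017 to April 30, 2018 is 212 days. At a uniform rate (an assumption) it holds about 1,483 × 212/1,673 = 188 of the 868 + 615 = 1,483 single-drug initiators, and fewer in practice because they must also start treatment by April 30, 2018. The number lost cannot be computed, so show it in the attrition table. On the half-widths in the working, losing even half the untreated cohort costs little precision.
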